9.10. Reporting of Unanticipated Risks or New Findings

Any unexpected Serious Adverse Events which occur during the course of this investigation and follow-up period, whether or not related to the study protocol, will be reported within 24 hours by telephone to NIDA (NIDA program official TBN), and the FRI IRB. The telephone report will be followed within 2 days by sending a completed Serious Adverse Event Form with demographic information and a narrative explanation of the event. The narrative will also provide details of relevant screening measures, medical history & physical, treatment compliance, participant reports of Serious Adverse Events and any other information the Principal Investigator deems appropriate. Attached to the Serious Adverse Event Form will be photocopies of relevant source documents (Case Report Forms). The Principal Investigator will address whether there is a need to redesign or amend the protocol, and/or to inform current and future participants of a change in description of risk, either in the consent form and protocol, or by other written or verbal communication. The written Serious Adverse Event report will also be sent to the FRI Institutional Review Boards.

The PI will also report any new information that may change the risk-benefit ratio to the FRI's IRB, medical safety monitor, and the NIDA Program Official. This information may consist of findings from the current study or other studies. Any changes in the protocol or informed consent as a result of this information will be promptly reported to the NIDA Program Official.

The PI will also report any irregularities in the conduct of the study, such as improper participant enrollment, obtaining of informed consent, and data collection or processing to the FRI's IRB, medical safety monitor, and the NIDA Program Official.

9.11. Quality Control of Data

Interviewers will be thoroughly trained regarding administration of interviews and completion of forms and their work will be reviewed on an ongoing basis. Interviewers will review case report forms (CRFs) for completeness and accuracy. Data processing staff will review CRFs the next day. The Project Manager will be advised of any forms needing correction, and he/she will bring these to the attention of the interviewer. Prior to the conduct of inferential analysis, the raw data will undergo extensive examination for completeness and accuracy by the data entry staff, under direction of the project's statistician.

9.12. Data and Safety Monitoring Board (DSMB)

As in our previous clinical trials of prison-initiated opioid agonist maintenance treatment, a DSMB of outside experts in clinical trials, biostatistics, and criminal justice (prisoner advocate) will be created to review the progress of the study and monitor subject intake, outcomes, adverse events and other safety related matters. The DSMB will meet at the start of study enrollment and every six months for the first year of enrollment and annually thereafter. Members will include a physician expert in the opioid treatment of opioid disorder, a statistician, and a criminal justice expert (prisoner advocate). The DSMB will review all SAEs. The project's statistician will perform interim analyses, at times determined by the DSMB, to determine whether the study should be terminated early as a result of preliminary findings. The Board will also review study enrollment and feasibility as well as the nature and frequency of SAEs in reviewing the safety of the study. DSMB meetings will be convened as needed to discuss new findings, unexpected SAEs related to the interventions under study, or results of any other new findings in the literature that pertain to this study. All DSMB reports will be sent to the PI who will forward copies to the IRB and to NIDA.

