6.7. Power. Stroup¹⁰¹ (also see Littell et al.¹⁰²) has outlined a four-step procedure to estimate power for general linear mixed models, which can also be applied to generalized linear mixed models as occur in the proposed study. This procedure was implemented in the current case. For each of the number of Times outcomes were measured (4, 5, 6, 7, or 9), three datasets for each hypothesis were created, assuming the dependent variable was continuous and normally distributed, discrete and Poisson distributed, or dichotomous and binomially distributed. For the normally distributed case, the only non-null effect in the model was the hypothesized effect of interest, with the XR-NTX-OTx condition mean set at 1 at Time 1, decreasing by .1 at each subsequent Time point, while the XR-NTX+MMTx condition means were set at 1 at Time 1, and then adjusted to reflect “small”¹⁰³ mean differences (.2 of the standard deviation at subsequent Time points) consistent with the hypothesis of interest. [Time was not included in the estimation of power for the criminal justice outcomes because these outcomes are measured only at 12-month post-baseline assessment.] Similar specifications were made for the datasets with outcomes following the Poisson and binomial distributions. Finally, observations were dropped from the data consistent with the expected loss of approximately 10% of participants at the 12-month assessment (see **Participant Attrition**, above). Hence, power was estimated for a design in which the effects were unbalanced in a manner similar to what was expected to occur in the proposed research. Therefore, simulations were conducted under what might be considered “worst-case scenarios.” Power was then estimated for three different covariance structures (compound symmetric heterogeneous, first-order autoregressive heterogeneous, and unstructured) of the observations over Time. [Covariance structures can be specified for GLiMM models independent of the location (e.g., mean) structure, so it was only necessary to create a single dataset for the three cases.] Assuming a sample size of 240 and $\alpha=.05$, the resulting power values ($1 - \beta$) for the Treatment Condition X Time effect varying between .81 and .85 in the simulations. From a more rudimentary and slightly less accurate perspective, assuming the primary outcome measures follow a normal distribution rather than binomial or Poisson distributions, power calculations based on the set correlation method¹⁰⁴ can be used to calculate effect sizes for desired power, including under the extremely conservative assumption that no other effect in the model is significant (with the resulting effect size estimates likely to be slight underestimates). In this case, assuming $\alpha=.05$ and $N=216$ due to attrition (see **Participant Attrition**, above) in order to remain conservative, an effect size of $f^2=.037$ in the population associated with a Treatment Condition main effect for statistical models in which there is no Time effect (e.g., reincarceration) and effect sizes ranging from a minimum $f^2=.046$ to a maximum $f^2=.072$ for the Treatment Condition X Time effects associated with the 4, 5, 6, 7, or 9 Time points for statistical models in which there is a Time effect, would yield a power of .8 for the respective effect. These effect sizes fall toward the “small-to-medium” range, with $f^2=.02$ considered a “small” effect and $f^2 = .15$ a “medium” effect.¹⁰³ In other words, and imprecisely, under the assumption that the effect in the population was $\geq .037$ or $\geq .072$, for the Treatment Condition and Treatment Condition X Time effects, respectively, there is an 80% chance of concluding that effect is significant if α is set to .05 and 216 participants are assessed at 12-month follow-up. *Power calculations do not utilize any estimates of treatment efficacy from prior studies. This latter approach to power analysis, although once popular, is often quite limited, as is the case for the proposed study, in that prior studies may have examined populations that are not comparable to the population in the proposed study and/or do not include the same experimental or control conditions, and in all cases, the effect sizes reported in prior studies are generally subject to wide fluctuation due to sampling variability.*¹⁰⁵ Power was calculated to detect a stated effect size, as detailed in the proposal, an approach consonant with more recent writings regarding power analysis.

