7.0. Project Timeline

Months 1-5 will be devoted to start-up activities, including confirming logistic arrangements, recruiting and training staff, and developing detailed procedures with prison and treatment personnel, and obtaining IRB and OHRP approval. Recruitment of participants and delivery of interventions will begin in month 6. Five to six prison inmate/participants are projected to be enrolled per month, yielding a total of 240 participants (120 per condition), at the end of recruitment (month 40). Follow-up assessments will be completed by month 53. Months 54-60 will be devoted to dissemination activities (e.g., publication of the primary outcomes paper).

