9.13. Criteria for Suspending or Terminating the Study

The study may be modified, suspended, or terminated at the recommendation of the PI, DSMB, or by the FRI IRB in the interests of protecting study participants. The study will be modified to comply with any labeling changes for long-acting naltrexone administration made by its manufacturer or by the Food and Drug Administration. The PI, medical safety monitor, DSMB and/or IRB may recommend modifying, suspending, or terminating the study based on the SAE reports. Trials may be terminated for any one or more of four classes of reasons as determined by the DSMB, as specified below: 1) safety/adverse events; 2) favorable benefit-risk ratio; 3) unfavorable benefit-risk ratio; and 4) inability to answer questions regarding trial efficacy.

9.13.1. Termination Due to Safety/Adverse Events. The DSMB's decision to stop the study with regard to safety/adverse event considerations will be based on the number and severity of study-related adverse events, particularly those determined to be fatal and/or extreme. The study may also be terminated if the DSMB decides that there has been an emergence of an unexpected serious adverse event or events.

9.13.2. Termination Due to Favorable Benefit-Risk Ratio. If the results of an interim analysis of post-release outcome data performed by the DSMB provides compelling evidence for the efficacy of the experimental intervention(s), early termination may be recommended. Such a recommendation would not be made without consideration of other relevant information related to the trial and an assessment of the strength of evidence of benefit.

9.13.3. Termination Due to Unfavorable Benefit-Risk Ratio. If the interim efficacy analysis results show compelling evidence for a lack of clinically relevant outcomes, early termination may be recommended by the DSMB. Such a recommendation would not be made without consideration of other relevant information related to the trial (e.g., safety/adverse event issues).

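### Interim efficacy analyses with stopping for benefit have no boundary or alpha spending, so overall type I error is not controlled at .05

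*Combined protocol and SAP*

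**What the plan says.** Section 9.12 states that the project's "statistician will perform interim analyses, at times determined by the DSMB, to determine whether the study should be terminated early". Section 9.13.2 shows that these are looks at efficacy: if an "interim analysis of post-release outcome data performed by the DSMB provides compelling evidence for the efficacy" of the experimental intervention, the board may recommend ending the trial. It adds that other relevant information and the strength of the evidence will be weighed. Section 9.13.3 provides for a stop when the interim efficacy results point to a lack of clinically relevant outcomes.

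Section 6 does not mention interim analyses. Section 6.7 uses alpha only as a planning value. For an effect of f² = .037 "in the population associated with a Treatment Condition main effect for statistical models in which there is no Time effect", it says that "there is an 80% chance of concluding that effect is significant", and the condition attached is that the effect is "significant if α is set to .05 and 216 participants are assessed at 12-month follow-up".

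The document gives no number of looks, information fractions, interim p-value, boundary or reduced final threshold. The aims list outcomes (a) to (f), and no outcome is named for the looks.

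On conduct, section 9.12 has the project's statistician run the looks, while section 9.13.2 has the DSMB perform them. Section 9.12 also says: "All DSMB reports will be sent to the PI".

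**The concern.** A trial that can stop for benefit at an interim look, and otherwise tests at the full .05 at the end, has more than one route to a positive claim. Under the null, the total false-positive probability is the .05 from the final test plus the probability of stopping for benefit in a trial that would not have been significant at the end. The second term is above zero for any workable stopping rule, so the total exceeds .05 unless the final threshold is lowered. An early stop for benefit also tends to exaggerate the estimated effect and disturbs the coverage of an ordinary confidence interval. This matters here because section 6.1 plans to report intervals and effect sizes.

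Since the plan states no threshold, a reader of the results could not work out what error rate a positive finding carries.

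**Working it through.** **1. The plan's own figure.** The inputs from section 6.7 are alpha .05, N = 216 and power .80, with f² = .037 for the treatment main effect. Using the noncentral F with u = 1 and v = 216 − 1 − 1 = 214, the noncentrality is λ = f²(u + v + 1) = .037 × 216 = 7.99. Power is .804, and the f² needed for exactly .80 is .0367, which rounds to .037. As a cross-check, d = 2√.037 = .385 with 108 per arm gives Φ(.385 × √(108/2) − 1.96) = Φ(.87) = .807. The figure reproduces, and only as a single final test that spends all of .05.

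**2. Overall type I error with interim looks.** Let Z₁, …, Z_K be the test statistics at information fractions t₁ < … < t_K = 1, with corr(Z_j, Z_k) = √(t_j/t_k). The overall error is P(|Z_k| > c_k for at least one k) under the null, found by recursive numerical integration. For one outcome, a two-sided test, equally spaced looks and the final test at .05:

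| Interim threshold | 1 interim | 2 interims | 3 interims | 4 interims |
|---|---|---|---|---|
| p < .001 | .0502 | .0505 | .0508 | .0511 |
| p < .01 | .0546 | .0585 | .0619 | .0650 |
| p < .05 | .0831 | .1073 | .1262 | .1417 |

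**3. How many looks the calendar would carry.** Section 7.0 starts recruitment in month 6, ends it in month 40 and completes follow-up by month 53. Section 9.12 has the board meet at the start, every six months in the first year and yearly after that, which is months 6, 12, 18, 30 and 42. Assume uniform accrual over 40 − 6 = 34 months, and 13 months from enrolment to the 12-month outcome (53 − 40 = 13). The information at month m is then (m − 13 − 6)/34:

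- months 6, 12 and 18: none
- month 30: 11/34 = .324
- month 42: 23/34 = .676

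That is two informative looks. With every look at .05, the overall error is .108.

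For a 6-month outcome available 7 months after enrolment, the information is 5/34 = .147 at month 18, 17/34 = .500 at month 30 and 29/34 = .853 at month 42. That is three looks, and the error is .131.

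**4. With a spending function.** The O'Brien-Fleming-type function with .025 per side spends 4[1 − Φ(2.241/√t)] by information t. At t = .324, .676 and 1 the boundaries are |z| = 3.77, 2.49 and 1.995 (nominal p = .00016, .0128 and .0461). Overall alpha is .0500. At the drift that gives .800 for a single test (1.960 + .842 = 2.802), power is .795. With four equally spaced interims the final nominal p is .0423 and power is .790.

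**5. With a fixed interim rule of p < .001.** To hold .05 overall, the final threshold must be about .0495 with two interims or .0489 with four.

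**The case against.** The strongest reply is that the plan never says looks are tested at .05. Section 9.13.2 asks for compelling evidence and for wider considerations, and a board that takes this to mean something like p < .001 would add almost nothing to the error rate. This stands as to size: the excess is unknown and may be negligible. It does not supply control, because a qualitative standard cannot be turned into an error rate.

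Alpha also appears only as a power assumption, and section 6.1 shifts emphasis from rejecting a null to direction, interval and effect size. Both are true. However, .05 is the only threshold the plan gives, and unadjusted looks affect the intervals and estimates too. Discretionary stopping under section 9.13.3 gives no dependable offset.

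A reader might go further in three ways that the documents do not support:

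- **Four looks and an error of .14.** Section 9.12 does not tie looks to meetings. Even if it did, only about two meetings carry 12-month data and three carry 6-month data. The re-arrest and re-incarceration records are collected at the end of the study.
- **Flexible timing as the defect.** A spending function allows times chosen by the board. What is missing is the rule.
- **The PI will receive interim efficacy results.** Section 9.12 sends all DSMB reports to the PI but does not say that they contain comparative efficacy data. It permits this and does not establish it.

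**Conclusion.** The point holds as a lack of control: efficacy looks with stopping for benefit are provided for, the full .05 is planned for one test, and nothing links the two. No particular inflation is established. For one outcome the total runs from .050–.051 (interims at p < .001), through about .055–.065 (p < .01, one to four interims), to about .11 for a 12-month outcome or .13 for a 6-month outcome (every look at .05, looks at the routine meetings).

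These figures assume a two-sided test, stopping in either direction, a final test at .05 and, for the last two, uniform accrual over months 6 to 40. The stated rate of five to six enrolments a month gives at most 35 × 6 = 210 over that span, even counting both end months. Recruitment to 240 could therefore run longer, and the number of informative looks could change. The figures do not cover testing several of outcomes (a) to (f) at a look.

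The disagreement over who runs the looks and the routing of DSMB reports are secondary clarifications. Neither changes the error rate.

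**What to change.** State in section 9.12 and in section 6 that any efficacy look is made on one named outcome with a Lan-DeMets O'Brien-Fleming-type spending function, and that the final critical value comes from the same function at the information actually observed. An example is |z| = 3.77, 2.49 and 1.995 at information .32, .68 and 1. Alternatively, require p < .001 at interims and lower the final threshold to about .0495 for two interims or .0489 for four. Keeping .05 at the end under that option leaves the total slightly above .05.

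Two clarifications should go with it. Sections 9.12 and 9.13.2 should name the same party to run the looks. Section 9.12 should say that any comparative interim efficacy results stay in a closed DSMB report that is not passed to the PI.

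The text is short, but the sponsor must first choose the outcome, which the aims do not do. Early stopping becomes harder, and with the spending function power falls from .800 to about .79 to .795 at unchanged sample size.

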9.13. Criteria for Suspending or Terminating the Study

The study may be modified, suspended, or terminated at the recommendation of the PI, DSMB, or by the FRI IRB in the interests of protecting study participants. The study will be modified to comply with any labeling changes for long-acting naltrexone administration made by its manufacturer or by the Food and Drug Administration. The PI, medical safety monitor, DSMB and/or IRB may recommend modifying, suspending, or terminating the study based on the SAE reports. Trials may be terminated for any one or more of four classes of reasons as determined by the DSMB, as specified below: 1) safety/adverse events; 2) favorable benefit-risk ratio; 3) unfavorable benefit-risk ratio; and 4) inability to answer questions regarding trial efficacy.

9.13.1. Termination Due to Safety/Adverse Events. The DSMB's decision to stop the study with regard to safety/adverse event considerations will be based on the number and severity of study-related adverse events, particularly those determined to be fatal and/or extreme. The study may also be terminated if the DSMB decides that there has been an emergence of an unexpected serious adverse event or events.

9.13.2. Termination Due to Favorable Benefit-Risk Ratio. If the results of an interim analysis of post-release outcome data performed by the DSMB provides compelling evidence for the efficacy of the experimental intervention(s), early termination may be recommended. Such a recommendation would not be made without consideration of other relevant information related to the trial and an assessment of the strength of evidence of benefit.

9.13.3. Termination Due to Unfavorable Benefit-Risk Ratio. If the interim efficacy analysis results show compelling evidence for a lack of clinically relevant outcomes, early termination may be recommended by the DSMB. Such a recommendation would not be made without consideration of other relevant information related to the trial (e.g., safety/adverse event issues).

11.0 APPENDIX (screening forms, medical forms, research instruments)
